Traditionally, low-calorie diets have been shown to be an effective strategy to reduce body weight and hepatic steatosis and, in turn, improve cardiometabolic health (7). However, energy-restricted approaches are still not a standard public health strategy due to their lack of long-term sustainability and some undesirable metabolic adaptations that certainly lead to weight regain even in highly motivated patients (8). Time-restricted eating (TRE) is a recently emerged intermittent fasting approach which has the potential to maximize the extensively reported beneficial metabolic effects of the energy intake restriction (9). TRE aims to maintain a consistent daily cycle of feeding (within a limited time window during ≤ 10 hours) and fasting (≥ 14 hours) to support healthy/consistent circadian rhythms (10). Irregular eating patterns and eating over an extended period of time may disrupt circadian rhythms and, thus, increase the risk of obesity and hepatic fat accumulation (11). Remarkably, recent studies in mice have concluded that TRE effectively reduces hepatic steatosis and improves cardiometabolic health (12), mainly through improved insulin sensitivity; yet, whether this strategy is similarly effective in humans remains still unclear.

Along with nutritional strategies, exercise has demonstrated its efficacy at reducing hepatic steatosis and at improving cardiometabolic health in humans (13–15). Furthermore, preliminary evidence has highlighted that the combination of TRE and exercise may normalize glucose homeostasis and improve lipid profile in women with overweight or obesity (16). Nevertheless, the differential effects of TRE combined with exercise and TRE or exercise alone on hepatic steatosis and cardiometabolic markers remain unknown.

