4.2. Sample size

Based on previous findings from a recent trial on the combination of alternate day fasting and exercise on hepatic fat content (67), we anticipate approximately 5.0% reduction in hepatic fat content in the TRE + Exercise group, 2.5% in the TRE group, 2.5% in the exercise group, and no significant change in this outcome in the usual-care group. Assuming a pre-post correlation of 0.8 and a standard deviation of 6 points in the main outcome, we estimate a medium effect size of 0.45. To detect this effect size as statistically significant in a one-way ANOVA with $\alpha = 0.05$ and a power of 0.8, a minimum of 19 patients per group is required. Accounting for subgroup analyses based on sex and a maximum dropout rate of 20%, we will aim to recruit ~46 participants for each trial group, resulting in a total sample size of ~184 participants, with ~92 women included. To ensure a balanced representation of both sexes and maintain an adequate sample size, we will implement several strategies:

- Recruitment Process: A specific recruitment process will be utilized to aim for an equal enrollment of men and women. For each woman recruited, we will encourage her to invite one man to participate in the study. This approach has been successfully employed in our previous intervention studies and has proven effective in achieving a balanced sex distribution (68–70).
- Sample size calculations: Our sample size calculations have taken into account subgroup analyses by sex. We have conservatively estimated a maximum dropout rate of approximately 20%. By considering this dropout rate, we have ensured that our study is adequately powered to detect the specified effect size even if there are differential dropout rates between men and women. For example, if men have a dropout rate of 5% and women have a dropout rate of 15%, our study will still have sufficient power to analyze the data separately in men and women.
- Expected dropout rate: While we have conservatively estimated the maximum dropout rate, we anticipate that the actual dropout rate will be relatively lower and similar between both sexes. This expectation is based on our previous studies and the measures we have to promote participant engagement and adherence (68–70).

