1.2. Objective

The overall objective is to investigate the effects of TRE combined with supervised exercise on hepatic fat content (primary outcome) and cardiometabolic health (secondary outcomes) in adults with obesity.

The primary objective is to investigate the effects of a 12-week TRE intervention combined with a supervised exercise intervention (TRE + Exercise), as compared with TRE (TRE) or supervised exercise alone (Exercise), and usual care control group (UC), on hepatic fat content (primary outcome) and cardiometabolic health (secondary outcomes) in adults with obesity.

Secondary aims are to:

- i. Investigate the effects of a 12-week TRE + Exercise intervention, as compared with TRE or supervised exercise alone, and UC, on other specific fat depots: abdominal visceral and subcutaneous adipose tissue, pancreatic fat and mid-thigh intermuscular and intramuscular adipose tissue, and body composition (fat mass and fat-free mass).
- ii. Investigate the effects of a 12-week TRE + Exercise intervention, as compared with TRE or supervised exercise alone, and UC, on cardiometabolic health markers including blood pressure, liver enzymes, glucose homeostasis, blood lipid profile, and circulating inflammatory biomarkers.
- iii. Investigate the effects of a 12-week TRE + Exercise intervention, as compared with TRE or supervised exercise alone, and UC, on fecal microbiota.
- iv. Investigate the effects of a 12-week TRE + Exercise intervention, as compared with TRE or supervised exercise alone, and UC, on sleep and physical activity patterns.
- v. Investigate the effects of a 12-week TRE + Exercise intervention, as compared with TRE or supervised exercise alone, and UC, on psychological outcomes (i.e., depression, stress and anxiety) and quality of life.
- vi. Investigate the effects of a 12-week TRE + Exercise intervention, as compared with TRE or supervised exercise alone, and UC, on physical fitness (i.e., cardiorespiratory fitness and muscular strength).
- vii. Examine the effect of a 12-week TRE + Exercise intervention, as compared with TRE or supervised exercise alone, and UC, on dietary habits and eating behaviour.
- viii. To quantify the persistence of the effects of TRE + Exercise intervention, TRE alone,

and supervised exercise alone on hepatic fat content and cardiometabolic health in the long-term (12-month follow-up).

2. Study methods

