2.3. Sample size

Based on previous findings from a recent trial on the combination of alternate day fasting and exercise on hepatic fat content,² we anticipate approximately 5.0% reduction in hepatic fat content in the TRE + Exercise group, 2.5% in the TRE group, 2.5% in the exercise group, and no significant change in this outcome in the usual-care group. Assuming a pre-post correlation of 0.8 and a standard deviation of 6 points in the main outcome, we estimate a medium effect size of 0.45. To detect this effect size as statistically significant in a one-way ANOVA with $\alpha = 0.05$ and a power of 0.8, a minimum of 19 patients per group is required. Accounting for subgroup analyses based on sex and a maximum dropout rate of 20%, we will aim to recruit ~46 participants for each trial group, resulting in a total sample size of ~184 participants, with ~92 women included.

Our sample size calculations have taken into account subgroup analyses by sex. We have conservatively estimated a maximum dropout rate of approximately 20%. By considering this dropout rate, we have ensured that our study is adequately powered to detect the specified effect size even if there are differential dropout rates between men and women. For example, if men have a dropout rate of 5% and women have a dropout rate of 15%, our study will still have sufficient power to analyse the data separately in men and women.

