2.4. Framework

A superiority hypothesis testing framework will be used. In the main analyses, we will compare whether TRE plus exercise interventions (TRE + Exercise group) is superior to TRE or Exercise alone or the UC (Mediterranean education program only).

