5.2. Analysis methods

The main analyses will consist of the intention-to-treat analyses for the primary and secondary outcomes using a constrained baseline (meaning baseline-adjusted) linear mixed model, which accounts for baseline differences among the study groups. The model will include fixed effects

for time (three levels) and treatment (four levels) as well as the unique participant identifier as a random effect, and sex will be included as a covariate. Model assumptions will be checked. In case we detect model violations, we will take appropriate measures by e.g., conducting data transformations. If the global test of significance indicates between-group differences, pairwise comparisons will be explored. Although no adjustments for multiplicity will be performed, family-wise type 1 error rate on the primary outcome will be retained by using a hierarchical analytic approach. The prespecified hierarchical hypotheses will be tested using the prespecified sequence: TRE + Exercise versus UC, TRE versus UC, Exercise versus UC, TRE + Exercise versus TRE, TRE + Exercise versus Exercise, and TRE versus Exercise. The main statistical analyses will be performed by an independent researcher ([name]), who is not involved in the recruitment, evaluations, and interventions, and will be performed blinded to the treatment allocation by coding the intervention arms (e.g., A, B, C, D).

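### If the hierarchy is read serially, TRE + Exercise vs TRE must wait on TRE vs UC, a gate that error control does not need; a closed test in the same order confirms more and keeps every serial rejection.

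*SAP*

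**What the plan says.** SAP 2.4 sets the main question: "we will compare whether TRE plus exercise interventions (TRE + Exercise group) is superior to TRE or Exercise alone or the UC". SAP 1.2 states the primary objective in the same terms.

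SAP 5.2, with the same sequence in Protocol 4.3, makes no multiplicity adjustment but says that the "family-wise type 1 error rate on the primary outcome will be retained by using a hierarchical analytic approach". After a significant global test, the contrasts are taken in an order that begins "TRE + Exercise versus UC, TRE versus UC, Exercise versus UC, TRE + Exercise versus TRE". Numbered in full, the steps are:

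1. TRE + Exercise vs UC
2. TRE vs UC
3. Exercise vs UC
4. TRE + Exercise vs TRE
5. TRE + Exercise vs Exercise
6. TRE vs Exercise

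No gating rule is written. SAP 3.1 sets two-sided tests at 0.05.

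**The concern.** A prespecified sequence is normally read as serial: each step counts only if every earlier step was significant. Two of the three comparisons that SAP 2.4 calls main, steps 4 and 5, then sit behind both single-intervention comparisons with UC.

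The order controls type I error and is not disputed. There is also a case for testing TRE against UC early, since the Protocol Introduction says of TRE that "whether this strategy is similarly effective in humans remains still unclear". But that uncertainty is also where a serial gate costs most. If TRE alone is weak, step 2 will often miss, and the trial then cannot claim that the combination beats TRE however clear that result is. The Introduction gives this as the knowledge gap: "the differential effects of TRE combined with exercise and TRE or exercise alone on hepatic steatosis and cardiometabolic markers remain unknown". A gate of this kind should be there because error control requires it.

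**Working it through.** **Inputs.** SAP 2.3 anticipates "approximately 5.0% reduction in hepatic fat content in the TRE + Exercise group, 2.5% in the TRE group, 2.5% in the exercise group" and no change in UC, with SD 6, pre-post correlation 0.8, a maximum of 20% dropout and 46 recruited per arm. The effects are read as percentage points of hepatic fat: 0, 2.5, 2.5 and 5.0.

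- Baseline-adjusted SD = 6 × √(1 − 0.8²) = 3.6, matching the constrained-baseline model.
- Change-score SD = 6 × √(2 × (1 − 0.8)) = 3.79, as a sensitivity value.
- n per arm = 46 with no dropout, or 46 × 0.8 = 36.8 at maximum dropout. Both are shown because Protocol 4.2 says "we anticipate that the actual dropout rate will be relatively lower and similar between both sexes".

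**The plan's own figure.** The stated means give f = √[(2.5² + 0 + 0 + 2.5²)/4] / 3.79 = 1.77/3.79 = 0.466, close to the stated 0.45. With f = 0.45, a four-group ANOVA reaches 80% power at 15 per group; at the stated 19, power is 91%. So 19 is not reproduced. Nothing below uses it.

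**Is the step 2 gate needed for step 4?** Write C = TRE + Exercise, T = TRE, E = Exercise, U = UC. Four arms can be grouped in 15 ways. One has all arms different, leaving 14 patterns with some equality. In a closed test, a contrast is confirmed when every pattern containing it is rejected. Test each pattern at 0.05 by the earliest SAP step that is null under it.

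| Patterns containing C = T | Tested by | Patterns containing C = E | Tested by |
|---|---|---|---|
| C = T = E = U | step 1 | C = T = E = U | step 1 |
| C = T = U | step 1 | C = E = U | step 1 |
| C = T = E | step 4 | C = T = E | step 4 |
| C = T and E = U | step 3 | C = E and T = U | step 2 |
| C = T only | step 4 | C = E only | step 5 |

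Step 4 therefore needs steps 1, 3 and 4, never step 2. Step 5 needs 1, 2, 4 and 5, never step 3. The same exercise gives {1}, {1, 2} and {1, 2, 3} for steps 1 to 3, unchanged from serial, and {1, 2, 4, 6} for step 6.

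Over all 64 combinations of significant and non-significant results, the closed test loses no serial rejection and gains at least one in 8.

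**Error rate.** Closure guarantees 5%. Simulated family-wise error over the 14 patterns was at most 5.05% for both rules (1,000,000 runs each). Wider searches over many configurations with fewer runs gave maxima near 5.2%, again for both rules and consistent with 5%. The step 3 gate must stay: dropping it as well gives 9.7% when C = T and E = U, against 4.9% for the closed test.

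**Power** (pooled-variance t tests, global F test required first under both rules). As a hand check on step 2 at 36.8 per arm: SE = 3.6 × √(2/36.8) = 0.84, and 2.5/0.84 = 2.98, which gives about 84% power.

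| Plan effects, SD 3.6 | 36.8 per arm: serial | closed | 46 per arm: serial | closed |
|---|---|---|---|---|
| TRE vs UC | 84% | 84% | 91% | 91% |
| Exercise vs UC | 75% | 75% | 85% | 85% |
| Combination vs TRE | 61% | 71% | 77% | 83% |
| Combination vs Exercise | 54% | 61% | 72% | 77% |
| At least one of these two | 61% | 78% | 77% | 88% |
| Both | 54% | 54% | 72% | 72% |

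In about 9% of trials (6% with no dropout), steps 1, 3 and 4 are all significant and only the TRE vs UC miss blocks step 4. With SD 3.79, at least one is confirmed in 54% vs 72% of trials (36.8 per arm) and 70% vs 84% (46 per arm).

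**Other effects (assumptions, not plan values), SD 3.6, serial vs closed:**

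| Assumed effects | Contrast | 36.8 per arm | 46 per arm |
|---|---|---|---|
| TRE 2.0, Exercise 2.5, combination 4.5 | vs TRE | 48% vs 71% | 64% vs 83% |
| TRE 1.0, Exercise 2.5, combination 3.5 | vs TRE | 14% vs 71% | 21% vs 83% |
| TRE 2.5, Exercise 1.0, combination 3.5 | vs Exercise | 4% vs 14% | 7% vs 21% |

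**The case against.** The plan contains no type I error. Fixed-sequence testing is standard and easy to explain, and the SAP never states the serial stop, so one sentence could settle the matter the other way. All of that is true. But the SAP's only stated reason for the hierarchy is family-wise control, and on that ground the step 2 gate does no work for step 4.

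If the aim is to beat both single interventions, the closed test gains nothing: 54% and 72% under either rule. That stands. The gain is in confirming one of the two, which the "or" in SAP 2.4 allows but does not require.

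Step 6 is also loosened. It is a true null under the plan's effects, and its false rejections rise from 0.8% to 2.2% at 36.8 per arm and from 1.6% to 3.0% at 46. This stands as a small cost inside the 5% family-wise level.

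Some results would be awkward to present. When step 2 misses, step 4 could be confirmed using the raw p value of step 3, while steps 2, 3 and 5 remain exploratory. One may also prefer to show that TRE works before claiming a benefit added to it. This is a fair question of interpretation, though the SAP does not give it as its reason, and step 1 must still show that the combination differs from UC.

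Finally, the largest gains rest on assumed effects, and timing matters. SAP version 2 is dated 01/07/2024 yet cites a 2025 reporting guideline, so the documents do not settle what was known when the text was finalised. A more permissive rule adopted after group results are known would look data-driven.

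**Conclusion.** The concern holds. The logic depends on no effect size or SD, only on all six contrasts being on the same scale and time point, which fits 12-week hepatic fat. The closed test is never less powerful for any contrast.

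At the plan's effects and SD 3.6, it adds 6 to 9 points for the combination vs TRE, 5 to 7 for the combination vs Exercise, and 11 to 17 for at least one of them. Those sizes assume the serial reading, effects in percentage points, and 36.8 to 46 analysed per arm. The cost grows sharply if TRE alone falls short of its planned 2.5 points. This should be changed, but the existing order does not invalidate the trial.

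**What to change.** Keep the order and write the gating rule into SAP 5.2 and Protocol 4.3. After a significant global test, a contrast is confirmed when its own raw p value and those of the listed steps are all below 0.05:

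| Step | Contrast | Also required |
|---|---|---|
| 1 | TRE + Exercise vs UC | none |
| 2 | TRE vs UC | 1 |
| 3 | Exercise vs UC | 1, 2 |
| 4 | TRE + Exercise vs TRE | 1, 3 |
| 5 | TRE + Exercise vs Exercise | 1, 2, 4 |
| 6 | TRE vs Exercise | 1, 2, 4 |

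Report contrasts that are not confirmed with 95% confidence intervals and label them exploratory.

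The cost is a few lines of text, and the change must be made and dated before unblinding. The six tests, their order and the 5% family-wise level stay the same, and decisions on steps 1 to 3 are identical. The rule is less familiar than stopping at the first failure, so the text should say that a contrast can be confirmed while a step it relies on remains exploratory.

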5.3. Missing data

The number of missing data will be reported, and patterns of missing data will be explored. Based on previous experience, we expect that missing data will be assumed as missing at random. Therefore, the linear mixed model analyses will handle our missing data. However, once the data processing is finalized, we will reconsider this assumption. In case we believe this assumption does not hold, we will take appropriate measures for the data analyses by using, for example, other multiple imputation techniques.

5.4. Additional analyses

Changes in other outcomes will be analyzed using a similar protocol as described by ‘5.2 Analysis methods’ unless other analyses would be more appropriate depending on the outcome (e.g., ordinal / dichotomous outcomes). Furthermore, cross-sectional analyses will be performed using the baseline data of the RCT. For example, cross-sectional associations will be explored by bivariate and partial correlations. Then, further analyses will be performed using linear and logistic regression depending on the nature of the study variables and research questions. ANOVAs will also be used to test differences in outcomes among groups.

5.5. Harms

The number and reasons of adverse events (e.g., headache, dizziness, falls, injuries, musculoskeletal problems, cardiovascular disease events, and any other events potentially related to the implementation of the trial protocol) at each time point will be collected, reported, and described separately for each study arm. No formal statistical testing will be undertaken.

5.6. Statistical software

The analyses will be performed using R. For the main analyses we will use the ‘lme4’ or ‘LMMstar’ package. The use of packages will be reported in the manuscript.

6. References

1. Camacho-Cardenosa A, Clavero-Jimeno A, Martin-Olmedo JJ, et al. Time-restricted

eating and supervised exercise for improving hepatic steatosis and cardiometabolic health in adults with obesity: protocol for the TEMPUS randomised controlled trial. *BMJ Open*. 2024;14(1):e078472. doi:10.1136/bmjopen-2023-078472

7. Summary of changes to Statistical Analysis Plan

Date	Amendment
01/07/2024	Review and improvement of the statistical analysis methods, including constrained baseline (meaning baseline-adjusted) linear mixed model.
01/07/2024	Update of secondary outcomes including new outcomes derived from magnetic resonance imaging, elastography, fasting urine, and fasting blood samples.
